**(3) Recurrence-Free Survival (RFS)**

The time interval (in months) from the date of initial surgery to the date of first pathologically confirmed local recurrence. Patients without recurrence are censored at the date of last follow-up.

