**(7) Distant Metastasis-Free Survival (DMFS)**

The time interval (in months) from the date of initial surgery to the date of first distant metastasis. Patients without metastasis are censored at the date of last follow-up.

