**(9) Overall Survival (OS)**

The time interval (in months) from the date of initial surgery to the date of death from any cause. Surviving patients are censored at the date of last follow-up.

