## **4. Study Population**

### **4.1 Inclusion Criteria**

(1) Patients with a postoperative paraffin-embedded pathology diagnosis of breast phyllodes tumor (benign, borderline, or malignant) according to WHO criteria.

(2) Patients who underwent surgical treatment at any participating center during the designated time period.

(3) Patients with complete or reasonably complete clinical records, pathology reports, and follow-up data sufficient to extract the core variables required by the study protocol.

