### **4.2 Exclusion Criteria**

(1) Patients with a postoperative pathological diagnosis of "phyllodes tumor, uncertain behavior" or with an unclassified grade.

(2) Patients with a history of prior malignant tumor (excluding breast cancer) for whom the time from curative treatment to study enrollment is <5 years, or the expected disease-free survival is <5 years, or who have other concurrent diseases that may affect the assessment of study endpoints.

(3) Patients lost to follow-up or with missing critical data (e.g., pathological grade, surgical procedure, follow-up outcomes).

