5.2 Study Flow Diagram

### 5.3 Methods to Reduce Bias

(1) **Standardized data collection** – All data extractors at participating centers will receive uniform training. Standardized Case Report Forms (CRFs) will clearly define each variable (e.g., “positive margin” defined as tumor cells present at the margin on pathology; “local recurrence” requires pathological confirmation) to reduce measurement and information bias.

(2) **Double independent extraction of key variables** – For primary outcome variables (recurrence, metastasis, death) and key exposure variables (pathological grade, surgical procedure, margin status), two researchers will independently extract data and cross-validate. Discrepancies will be adjudicated by a third senior researcher.

(3) **Clear inclusion/exclusion criteria** – Strict definitions will avoid selection bias. All eligible consecutive cases will be enrolled; no sampling based on outcome or exposure.

(4) **Handling of missing data** – Cases with >20% missing key variables will be excluded. For variables with  $\leq 20\%$  missingness, multiple imputation ( $m=5$ ) will be used. Results from complete case analysis and imputed analysis will be compared to assess missingness bias.

(5) **Confounding control** – Multivariable regression models will adjust for known prognostic factors (age, tumor size, pathological grade, margin status, etc.). For non-randomized treatment comparisons (e.g., different surgical procedures), propensity score matching (PSM, caliper =  $0.2 \times \text{SD of PS}$ ) or inverse probability of treatment weighting (IPTW) will be used to balance covariates. E-values will be calculated to evaluate the strength of unmeasured confounding.

(6) **Control of multicenter heterogeneity** – Center effects will be adjusted using Cox shared frailty models or generalized estimating equations (GEE) with center as a random effect.

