### **(5) Bias control (as described in 5.3) – PSM, IPTW, E-value.**

### **(6) Stratified, subgroup, and sensitivity analyses**

- **Stratified analysis:** All primary analyses will be stratified by pathological grade (benign/borderline/malignant) to compare prognostic factors across grades.
- **Pre-specified subgroups:** Age (<35 vs. ≥35 years), tumor size (<5 cm vs. ≥5 cm), surgical procedure (segmental resection vs. minimally invasive rotary

excision, wide local excision vs. total mastectomy). Forest plots will display subgroup HRs with interaction P-values.

- **Sensitivity analyses:**
  - Complete case analysis vs. multiple imputation.
  - Varying PSM parameters (1:1 vs. 1:2 matching, caliper 0.1 vs. 0.2).
  - Separate analysis of recurrence definitions (ipsilateral chest wall/axilla only) to exclude misclassification.
  - Excluding patients with follow-up <6 months.
  - For OS, competing risk analysis with death from PT vs. other causes.

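### Exclusion 4.2(3) makes cohort entry depend on undefined follow-up completeness, contradicts the plan's own censoring rules, and can inflate recurrence, metastasis and mortality estimates

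*Combined protocol and SAP*

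**What the plan says.** **Who enters the cohort**

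- 4.2(3) excludes "Patients lost to follow-up or with missing critical data (e.g., pathological grade, surgical procedure, follow-up outcomes".
- 4.1(3) has the matching inclusion condition: records must include "follow-up data sufficient to extract the core variables required by the study protocol". It gives no minimum length of follow-up.
- 5.3(3) states: "All eligible consecutive cases will be enrolled; no sampling based on outcome or exposure".

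**How incomplete follow-up is handled elsewhere**

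- 3.2.1(3), recurrence-free survival: "Patients without recurrence are censored at the date of last follow-up".
- 3.2.1(7), distant metastasis-free survival: "Patients without metastasis are censored at the date of last follow-up".
- 3.2.1(9), overall survival: "Surviving patients are censored at the date of last follow-up".
- 6.2.3 names follow-up outcomes among the critical variables. Where they cannot be recovered, they are to be recorded as missing and their effect assessed in the analysis.
- 5.4.2(6) lists, as a sensitivity analysis only, "Excluding patients with follow-up <6 months".

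**Denominators and sources**

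- 3.2.1(2) and 3.2.1(6) define the local recurrence (LR) and distant metastasis (DM) rates as percentages of the whole study population, that is, after exclusions.
- 6.1.2 takes all data from the hospitals' own information systems. No death-registry linkage or active contact is described.
- The plan gives no definition of loss, no follow-up cut-off date and no expected loss share.

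**The concern.** Eligibility should be settled by what is known at surgery. Here it also depends on whether follow-up later stayed complete, which can be related to the outcome. Kaplan-Meier and cumulative incidence methods exist so that a patient seen for three years and then no more can contribute those three years. Excluding that patient discards valid event-free person-time.

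The estimates at stake are the study's main product: LR, DM and overall survival (OS), overall and by grade. Comparisons between grades, periods and centres could also be distorted if loss differs between them, though the documents give no information on that. With loss undefined, eight centres could apply the rule in eight ways.

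The planned checks do not reach the problem. The comparison of complete-case with imputed results runs on the cohort left after exclusion, and no sensitivity analysis puts the excluded patients back.

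**Working it through.** **1. The plan's own figure.** 5.4.1 expects about 380 LR events from about 3,500 patients at about 11%. 3,500 × 0.11 = 385. With the 7:2:1 grade mix and the grade-specific rates in 2.1, 0.7 × 7.1% + 0.2 × 16.7% + 0.1 × 25.1% = 10.82%, or 379 events. The figure is reproduced, and the sample size arithmetic is not in question.

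**2. One patient under each rule.** Take a patient seen recurrence-free for three years and then no more.

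- 3.2.1: contributes 36 months and is censored.
- 4.2(3): out of the cohort, if this counts as lost.
- 6.2.3: if the final outcome counts as missing, stays in and is flagged.
- 5.4.2(6): stays in, even in the sensitivity analysis, because follow-up exceeds six months.

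These cannot all apply.

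**3. Three readings of the exclusion.**

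- (a) Event-free patients with incomplete follow-up are removed; patients with a recorded event stay.
- (b) Everyone later lost is removed, including patients who had a recurrence or metastasis first.
- (c) Only patients with no contact at all after surgery are removed.

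The Kaplan-Meier risk is 1 − Π(1 − d/n) over event times, with d events among n at risk. Under (a), d is unchanged and n falls, so the risk rises. Under (b), if loss is independent of the event, d and n shrink in proportion and the risk is unchanged. Under (c), the removed patients have no person-time, so nothing changes if they are a random subset.

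**4. Size, by simulation.** Inputs:

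- The true 10-year LR risk is 11%. This is the 5.4.1 rate; reading it as a 10-year risk is an assumption. The hazard is −ln(0.89)/10 = 0.01165 per year, with exponential times (assumed).
- Potential follow-up is uniform from 1 to 24 years. Surgery dates of 2001 to 2023 come from 5.1; the cut-off at the end of 2024 is assumed.
- Loss is exponential and independent of the event, with 5%, 10% or 20% lost by year 5 (assumed). The loss hazards are −ln(0.95)/5 = 0.0103, −ln(0.90)/5 = 0.0211 and −ln(0.80)/5 = 0.0446.

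| Removed event-free | 10-year LR, censoring at last contact | 10-year LR, reading (a) | Ratio to 11% |
|---|---|---|---|
| about 11% | 11.0% | 12.0% | 12.0/11 = 1.09 |
| about 20% | 11.0% | 13.1% | 13.1/11 = 1.19 |
| about 37% | 11.0% | 15.6% | 15.6/11 = 1.42 |

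Repeat runs agree to about 0.1 percentage point. Readings (b) and (c) return 11.0% to 11.1% throughout. For a rarer event with an assumed 10-year risk of 3%, reading (a) gives 3.2%, 3.5%, 3.9% and 4.4% when 10%, 20%, 30% and 40% are removed.

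**5. Overall survival.** A patient whose death is recorded cannot afterwards be lost; a survivor can. For OS, therefore, reading (b) collapses into reading (a). An assumed true 10-year mortality of 5% becomes about 6.0% when about 22% are removed (6.0/5 = 1.20). Only reading (c) avoids this.

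**6. Crude rates.** 380/3,500 = 10.9%. If those 3,500 were what remained after 20% had been removed event-free, the source cohort would be 3,500/0.8 = 4,375, and 380/4,375 = 8.7%. Neither is a sound risk estimate. The first omits event-free patients, and the second counts patients of unknown status as event-free.

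**7. The six-month rule.** It acts on length of follow-up, not on event time. A patient who recurs at month 3 and is followed to year 2 stays. A patient who dies before month 6 leaves. With time still counted from surgery, the OS curve then shows no deaths in the first six months.

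**The case against.** A reader might infer that patients with events always stay, so that every LR, DM and OS estimate is biased upward. The documents do not support that. 4.2(3) makes no exception for patients with events; read literally, a patient who recurs and is later lost is also excluded. Under that reading LR and DM are unbiased if loss is independent of the event. If only patients never seen after surgery are meant, and they are a random subset, no estimate is biased.

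The plan also offers some support for the narrow reading. 4.2(3) lists loss beside missing outcomes, which suggests absent data. Dropping short follow-up only as a sensitivity analysis implies that such patients are otherwise in the cohort. The censoring rules are stated three times. It would therefore be wrong to say that the plan simply deletes patients instead of censoring them.

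The sizes above also rest on assumed loss shares and an assumed cut-off. The pooled 12.6% recurrence rate in 2.2.2 has no time horizon and cannot serve as a 10-year risk.

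All of that stands as a limit on size and certainty. It does not remove the contradiction, because the harmless reading is nowhere stated. For LR, independence is also doubtful: 3.2.1(1) requires pathological confirmation from hospital records, so a recurrence itself generates contact. For OS, the second reading gives no protection.

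The rule "Cases with >20% missing key variables will be excluded" and the number of imputations in 5.3(4) are separate missing-data questions and add nothing to this point.

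**Conclusion.** The concern holds as a contradiction around an undefined term, with a possible bias that no planned analysis would reveal. The text as written selects patients on post-surgery information, against the censoring rules in 3.2.1 and the missing-outcome rule in 6.2.3. It also sits poorly with the assurance in 5.3(3).

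If event-free patients with incomplete follow-up are removed and recorded events kept, the relative inflation of 10-year LR is about 9% to 42% for removal of about 11% to 37% of the cohort. This assumes exponential times, independent loss and 1 to 24 years of potential follow-up. OS is the clearest case. For LR and DM the bias may be nil under the second reading, and for all three endpoints under the no-contact reading.

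If loss is related to outcome, bias could go in either direction, and censoring alone would not fully cure it. The actual size cannot be determined from the documents.

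**What to change.** 1. In 4.2(3), delete loss to follow-up and missing follow-up outcomes as grounds for exclusion. In 4.1(3), delete the follow-up condition.
2. Keep every otherwise eligible operated patient and censor at last documented contact, as 3.2.1 already says.
3. State the follow-up cut-off date and define loss.
4. Report the number of patients with no post-surgery contact, by grade and centre.
5. Base LR and DM rates on Kaplan-Meier or cumulative incidence estimates instead of the crude percentages in 3.2.1(2) and 3.2.1(6). Otherwise the retained lost patients would count as non-events and pull the rates down.
6. Replace the six-month exclusion in 5.4.2(6) with a 6-month landmark analysis, with time counted from month 6 and results described as conditional on reaching it. Requiring six months of potential follow-up would not be a substitute: surgery ends on 31 December 2023, so a cut-off at the end of 2024 would exclude nobody.
7. Optionally, add a sensitivity analysis for informative loss, such as inverse probability of censoring weights.

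The cost is mainly wording, plus less complete records and slightly more analysis work. The cohort definition should be settled before the database lock described in 6.2.4.

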## **5. Study Design**

### **5.1 Overall Design**

[figure not shown]
This is a multicenter, retrospective cohort study. Data will be collected from patients who underwent breast surgery at the Departments of Breast Surgery of the following eight participating centers between January 1, 2001, and December 31, 2023:

- Sun Yat-sen Memorial Hospital, Sun Yat-sen University
- The First People's Hospital of Foshan
- Sun Yat-sen University Cancer Center
- Peking University Shenzhen Hospital
- Foshan Women and Children's Hospital
- The First Affiliated Hospital of Guangzhou Medical University
- Zhongshan People's Hospital
- Shanwei People's Hospital

The expected sample size is approximately 3,500 patients. Using real-world data over nearly 20 years, the study will systematically describe the clinicopathological characteristics, treatment patterns, and long-term prognosis of breast PT in China, and identify independent risk factors through descriptive analysis, propensity score methods, competing risk models, and sensitivity analyses.

5.2 Study Flow Diagram

### 5.3 Methods to Reduce Bias

(1) **Standardized data collection** – All data extractors at participating centers will receive uniform training. Standardized Case Report Forms (CRFs) will clearly define each variable (e.g., “positive margin” defined as tumor cells present at the margin on pathology; “local recurrence” requires pathological confirmation) to reduce measurement and information bias.

(2) **Double independent extraction of key variables** – For primary outcome variables (recurrence, metastasis, death) and key exposure variables (pathological grade, surgical procedure, margin status), two researchers will independently extract data and cross-validate. Discrepancies will be adjudicated by a third senior researcher.

(3) **Clear inclusion/exclusion criteria** – Strict definitions will avoid selection bias. All eligible consecutive cases will be enrolled; no sampling based on outcome or exposure.

(4) **Handling of missing data** – Cases with >20% missing key variables will be excluded. For variables with  $\leq 20\%$  missingness, multiple imputation ( $m=5$ ) will be used. Results from complete case analysis and imputed analysis will be compared to assess missingness bias.

(5) **Confounding control** – Multivariable regression models will adjust for known prognostic factors (age, tumor size, pathological grade, margin status, etc.). For non-randomized treatment comparisons (e.g., different surgical procedures), propensity score matching (PSM, caliper =  $0.2 \times \text{SD of PS}$ ) or inverse probability of treatment weighting (IPTW) will be used to balance covariates. E-values will be calculated to evaluate the strength of unmeasured confounding.

(6) **Control of multicenter heterogeneity** – Center effects will be adjusted using Cox shared frailty models or generalized estimating equations (GEE) with center as a random effect.

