### **6.2.3 Data Integrity Checks**

- **Source Data Verification (SDV):** The project team will randomly select 10% of cases. A quality control officer will compare the data in the eCRF with the original hospital electronic medical records item by item to ensure transcription accuracy.
- **Logical Checks:** Logic validation rules will be embedded at the database design stage (e.g., surgery date cannot be later than recurrence date; tumor size cannot be negative). The system will automatically flag data points that violate logic, requiring mandatory review.
- **Missing Value Management:** The system will generate regular missing value reports. For critical variables (e.g., pathological grade, surgical margin status, follow-up outcomes), every effort will be made to trace back to medical records for supplementation. If supplementation is truly impossible, the value will be clearly recorded as "missing" and its impact will be assessed in subsequent statistical analyses.

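### Sections 4.2(3), 5.3(4) and 6.2.3 do not agree on whether a patient with a missing critical variable is excluded or kept, and the planned missingness check cannot see the selection that exclusion causes

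*Combined protocol and SAP*

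**What the plan says.** Three sections deal with a missing important variable.

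- Section 4.2(3), an exclusion criterion, removes "Patients lost to follow-up or with missing critical data (e.g., pathological grade, surgical procedure, follow-up outcomes". It gives no threshold, and its list is open.
- Section 5.3(4) sets a threshold for cases: "Cases with >20% missing key variables will be excluded". For variables with at most 20% "missingness, multiple imputation ( $m=5$ ) will be used". It then states: "Results from complete case analysis and imputed analysis will be compared to assess missingness bias". Section 5.4.2(6) repeats that comparison as a sensitivity analysis.
- Section 6.2.3 lists grade, margin status and follow-up outcomes as examples of critical variables and asks for them to be traced in the records. Where that fails, "the value will be clearly recorded as 'missing' and its impact will be assessed in subsequent statistical analyses".

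Five other places bear on the point. Sections 4.1(1) and 4.2(1) together require a tumour graded benign, borderline or malignant. Section 4.1(3) asks for records that are complete or reasonably so, without defining the term. Section 5.3(2) names six variables for double extraction: recurrence, metastasis, death, grade, procedure and margin status. Section 3.2.2(12) codes margin only as negative or positive, plus a distance. Section 5.3(3) assures the reader: "All eligible consecutive cases will be enrolled; no sampling based on outcome or exposure".

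**The concern.** A patient's membership of the cohort depends on which section is applied to her. Grade is the exception, since 4.1(1) and 4.2(1) require it; there, 6.2.3 merely needs aligning. For procedure and margin nothing else in the text settles the matter.

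The choice matters because exclusion for a missing report selects patients on how well they were documented. Over 23 calendar years and eight hospitals, documentation may well vary with period and centre, although the documents do not say so. The results most exposed are the descriptive ones in Section 3.1.2: the grade distribution, the treatment trends over two decades, and the recurrence, metastasis and mortality rates. The assurance in 5.3(3) does not help, because it covers only patients who have already been found eligible.

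**Working it through.** **1. The plan's own figure.** Section 5.4.1 gives 3,500 patients, about 11% local recurrence and about 380 events. 3,500 × 0.11 = 385. With its 7:2:1 grade split and the rates by grade in Section 2.2.2: 0.7 × 7.1% + 0.2 × 16.7% + 0.1 × 25.1% = 10.82%, and 3,500 × 0.1082 = 378.7. Both agree with 380, so that figure is not in dispute.

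**2. The rules side by side**, for a patient with one item missing. The 5.3(4) column takes the six variables of 5.3(2) as the denominator.

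| Missing item | 4.1 / 4.2 | 5.3(4) | 6.2.3 |
|---|---|---|---|
| Procedure | Excluded, named in 4.2(3) | Kept, imputed | Not named; list open |
| Margin | Not named; list open | Kept, imputed | Named; recorded as missing, analysed |
| Grade | Excluded by 4.1(1), 4.2(1), 4.2(3) | Kept, imputed | Named; recorded as missing, analysed |
| Follow-up outcome | Excluded, named in 4.2(3) | Kept, imputed | Named; recorded as missing, analysed |

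The last two columns are compatible: a value can be recorded as missing and then imputed. The opposition is between the first rule column and the other two.

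**3. Dependence on the denominator.** One missing of six is 1/6 = 16.7%, so kept; two of six is 33.3%, so excluded. With five variables, 1/5 is exactly 20%, which is not above 20%, so kept. With four, 1/4 = 25%, so excluded. Adding age and tumour size from 5.3(5) to the six gives 1/8 = 12.5%, so kept. The conflict over a single missing item therefore exists for any list of five or more, and vanishes for four or fewer.

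**4. Patients whose status changes (illustration).** Assume that grade and outcomes are known, that procedure and margin are each missing with probability q, and that they are missing independently. A patient missing only procedure is excluded by 4.2(3) and kept by 5.3(4): 3,500 × q(1 − q). If a site also reads margin as critical, the number doubles.

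| q (assumed) | Procedure only | Procedure or margin, not both |
|---|---|---|
| 1% | 35 | 69 |
| 2% | 69 | 137 |
| 5% | 166 | 333 |
| 10% | 315 | 630 |

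**5. Possible effect on the recurrence rate (illustration).** Let a share e be excluded, let the kept patients have the plan's 11%, and let the excluded have r times that rate. The full-cohort rate is 11% × [(1 − e) + e·r], so the kept cohort errs by 11% × e(1 − r).

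| e (assumed) | r = 0.5 | r = 1 | r = 2 |
|---|---|---|---|
| 5% | +0.28 points | 0 | −0.55 points |
| 10% | +0.55 points | 0 | −1.1 points |
| 20% | +1.1 points | 0 | −2.2 points |

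**6. Why the planned check misses this.** A patient removed at eligibility enters neither the complete-case nor the imputed analysis, so the difference between the two cannot depend on her. If 4.2(3) is applied strictly, no patient with missing procedure remains. The two analyses then hold the same procedure data, and agreement on that variable carries no information about the exclusions. No comparison of excluded with included patients is planned.

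**The case against.** The best defence is that the sections work in sequence: Section 4 settles eligibility, Section 5.3(4) deals with remaining gaps, and 6.2.3 is a data-management step that decides nobody's eligibility. Uniform training and standard CRFs (5.3(1)), a data dictionary and central monitoring (6.2.4) would then keep centres consistent. The study flow diagram is not reproduced in the text reviewed and may show the order.

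Part of this stands. A reader might infer three mutually opposed eligibility rules; the documents do not support that, because only 4.2(3) is an eligibility rule and the other two are compatible. But the text does not state the sequence. On that reading 6.2.3 would also have no missing grades or outcomes left to assess. Training and a dictionary can apply a rule, but they do not choose one. Even in sequence, the exclusion comes before the check.

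Other stronger readings also fail:

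- **The 16.7% is the plan's own figure.** It is not. Section 5.3(2) lists variables for double extraction and does not call them the base of the 20% rule.
- **Missing grade should be imputed.** That would contradict 4.1(1) and 4.2(1).
- **The rotary-excision subgroup would lose its patients because margins cannot be read there.** No section says anything about margin assessability after that procedure, and 4.2(3) does not name margin.
- **Exclusions will fall mainly on benign, early or small-centre cases and shift the grade mix by a known amount.** The documents give no missingness pattern.

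**Conclusion.** The concern holds as a conflict between excluding and keeping, together with a check that cannot detect selection by exclusion. Both follow from the wording and need no assumed rate. The exception is the contrast between 4.2(3) and 5.3(4) for a single missing item, which requires a key-variable list of five or more.

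The size is unknown. The counts in step 4 and the shifts in step 5 rest on assumed missingness, independence and rate ratios. They show that the number of patients affected could be appreciable while the shift in the overall recurrence rate stays modest; with r = 1 that shift is zero. Whether 3,500 is counted before or after exclusions is also unclear. If before, a 20% loss would leave 385 × 0.8 = 308 events, or 308/40 = 7.7 per variable at 40 variables, against 380/40 = 9.5 as planned. If after, there is no such loss.

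This should be corrected before extraction, since patients who are never entered cannot be recovered in the analysis.

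**What to change.** Write one rule and use it in 4.2(3), 5.3(4) and 6.2.3, with 4.1(3) referring to it.

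- Keep the requirement for a classified grade and add a known date of initial surgery. Align 6.2.3 with this by removing grade from the values that may stay missing.
- Do not exclude for missing procedure, margin or other covariates. Delete the 20% case-exclusion rule, and say what is done with a variable that is more than 20% missing, on which 5.3(4) is silent.
- Impute those covariates with the event indicator, cumulative hazard, year of surgery and centre in the imputation model.
- Extend the margin item so that a margin that could not be assessed and a margin that was not reported are recorded separately. The first is a finding; the second is a missing value.
- Keep complete-case analysis as the sensitivity analysis. Report exclusions by reason, centre and period, and compare excluded with included patients on what is known of both.
- Leave 4.2(2) unchanged. Loss to follow-up is a separate question, but whatever rule is adopted for missing outcomes must read the same in 4.2(3) and 6.2.3.

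The cost is redrafting in a few sections, one extended eCRF item, a short table of exclusions and some extra imputation work. The drawback is more imputed values, probably for patients from the early years.

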### 5.4 Statistical Analysis

#### 5.4.1 Sample Size and Justification

This is a retrospective cohort study; sample size is not based on a pre-specified effect size. All eligible patients with breast PT from the eight centers between January 1, 2001, and December 31, 2023, will be included. Based on each center’s historical annual

caseload and pathology database searches, approximately **3,500 patients** are expected (benign:borderline:malignant  $\approx$  7:2:1).

This sample size is the largest multicenter real-world study in the PT field to date. According to the EPV (events per variable) rule, with local recurrence as the primary endpoint (estimated overall recurrence rate  $\sim$ 11%, yielding  $\sim$ 380 events), the sample size supports multivariable analysis of 30–40 independent variables, fully meeting the requirements for prognostic factor screening.

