#### **5.4.2 Statistical Analysis Plan**

Statistical analyses will be performed using R version 4.2.0 or higher (key packages: tidyverse, survival, rms, tableone, MatchIt, mice, tidycmprsk, mstate, etc.). The significance level  $\alpha = 0.05$  (two-sided), and 95% confidence intervals will be reported.

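### Five imputations, with no stated seed or Monte Carlo error check, leave borderline p-values and confidence limits for heavily imputed covariates dependent on the random seed (minor)

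*Combined protocol and SAP*

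**What the plan says.** Section 5.3 (4) sets two missing-data rules. At patient level, "Cases with >20% missing key variables will be excluded". For variables with no more than 20% of values missing, "multiple imputation ( $m=5$ ) will be used". The number five is not justified, and nothing in the document fixes a seed, asks for Monte Carlo error or FMI to be reported, or allows m to rise.

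The only check on the imputation is in the same item: "Results from complete case analysis and imputed analysis will be compared to assess missingness bias". Section 5.4.2 (6) repeats it as a sensitivity analysis: "Complete case analysis vs. multiple imputation".

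Section 4.2 (3) limits what can be imputed, because it excludes "Patients lost to follow-up or with missing critical data (e.g., pathological grade, surgical procedure, follow-up outcomes", among others. Tumor size and margin status are not among those examples, and section 5.3 (5) names both as adjustment variables. Section 5.4.2 sets alpha at 0.05 ("two-sided), and 95% confidence intervals will be reported"). Section 5.4.2 (4) selects variables by AIC or LASSO and applies Bonferroni correction to multiple exposure comparisons within an endpoint.

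**The concern.** Multiple imputation draws random values, so a second run with another seed gives a slightly different estimate, standard error and p-value. The usual defence of m=5 is the efficiency of the point estimate. That does not answer whether a reported p-value or confidence limit would be reproduced by someone repeating the analysis.

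The planned comparison of complete-case with imputed results cannot answer it either. It is aimed at missingness bias, and with m=5 part of any difference it shows may be seed noise. At stake is whether a borderline imputed covariate is reported as an independent prognostic factor for a reason unrelated to the patients.

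**Working it through.** **The plan's own figure.** Section 5.4.1 says "approximately 3,500 patients are expected" and puts the "estimated overall recurrence rate" at about 11%, giving about 380 events and 30 to 40 variables.
- 3,500 × 0.11 = 385 events, in line with about 380.
- Weighting the background recurrence rates by the 7:2:1 grade mix: 0.7 × 7.1% + 0.2 × 16.7% + 0.1 × 25.1% = 10.8%, or 379 events.
- At ten events per variable, 380 / 10 = 38 variables.

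The figure reproduces. The plan thus envisages models with many covariates.

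**Inputs for the check.** From the plan: m=5, a 20% limit per variable, and two-sided alpha 0.05. Assumed: FMI of 0.05, 0.1 or 0.2. To see whether 0.2 is reachable, one cohort was simulated with 3,500 patients, 346 events, a logistic outcome model and three covariates each 20% missing at random. FMI was 0.18 to 0.22 for those three covariates and at most 0.03 for the fully observed ones. FMI 0.2 is therefore about the plan's upper limit.

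**Formulas.** In units of the standard error, the seed-to-seed SD of the pooled estimate is √(FMI/m). Relative efficiency is 1/(1 + FMI/m).
- FMI 0.2, m=5: √(0.2/5) = 0.20 SE; efficiency 1/1.04 = 96%.
- FMI 0.1, m=5: √(0.1/5) = 0.14 SE; efficiency 1/1.02 = 98%.
- FMI 0.05, m=5: √(0.05/5) = 0.10 SE; efficiency 1/1.01 = 99%.
- FMI 0.2, m=20: √(0.2/20) = 0.10 SE. With m=50: √(0.2/50) = 0.063 SE.

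**P-values across seeds.** Rubin's rules with Barnard-Rubin degrees of freedom were simulated, letting the between-imputation variance vary as well. The stable p is the value that very many imputations would give. If a run is significant with probability s, two runs disagree with probability 2s(1 − s). For stable p = 0.03, FMI 0.2 and m=5, s = 0.71 and 2 × 0.71 × 0.29 = 0.41.

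Chance that two seeds disagree on p<0.05, for stable p = 0.03:

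| FMI | m=5 | m=20 | m=50 |
|---|---|---|---|
| 0.05 | 7% | <1% | <1% |
| 0.1 | 24% | 1% | <1% |
| 0.2 | 41% | 11% | 1% |

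Other stable p-values at FMI 0.2:

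| Stable p | m=5 | m=20 | m=50 |
|---|---|---|---|
| 0.01 | 7% | <1% | <1% |
| 0.02 | 24% | 1% | <1% |
| 0.05 | 49% | 50% | 50% |

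At FMI 0.2 the coefficient of variation of the confidence-interval half-width is 9.8% with m=5, 3.5% with m=20 and 2.1% with m=50.

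**Cross-check in the simulated cohort.** One covariate with 20% missing had a stable p of 0.207. The 5th to 95th percentile of p across seeds was 0.115 to 0.365 with m=5 and 0.173 to 0.246 with m=50. Grade and age were significant in every run with m=5.

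**The case against.** The strongest reply is that little depends on this. Section 3.1.3 lists the search for independent prognostic factors as exploratory. Patients without grade, procedure or outcome are excluded, so the cumulative rates overall and by grade use no imputed values. Section 6.2.3 asks for missing critical values, including margin status, to be traced in the records. If margin status also counts as critical for exclusion, the point applies only to the other imputed covariates. All of this stands, and it keeps the point minor.

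Four stronger readings are tempting, but the documents do not support them.

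- **FMI near 0.5.** If six or eight covariates were each 10% missing independently, 1 − 0.9⁶ = 47% or 1 − 0.9⁸ = 57% of patients would be incomplete, and a reader might take that share for the FMI. It is not: in the simulated cohort 48% of patients were incomplete, yet FMI reached only 0.22. Those shares also ignore the patient-level exclusion. If the six or eight covariates are the key variables (the plan does not list them), anyone missing two is removed, since 2/6 = 33% and 2/8 = 25%. The incomplete share among retained patients is then 0.354/(0.531 + 0.354) = 40%, or 0.383/(0.430 + 0.383) = 47%.
- **A larger m removes the noise.** It only narrows the unstable zone. A factor exactly at 0.05 flips about half the time at any m.
- **AIC or LASSO selection is shown to be unstable.** The plan does not say how selection is combined across imputed data sets, but no selection instability was calculated here. Nor is selection itself a screen at 0.05.
- **The imputation model is misspecified.** Whether it includes the event indicator and cumulative hazard is a separate matter, on which the plan is silent.

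**Conclusion.** The point holds as a minor reproducibility weakness. It concerns covariates that are actually imputed at rates near the 20% limit and whose p-values lie roughly between 0.01 and 0.10. For a stable p of 0.03, two seeds disagree at 0.05 about 41% of the time with m=5 at FMI 0.2, and 24% at FMI 0.1. At about 5% missingness, m=5 is nearly adequate. Where a Bonferroni threshold applies, the same noise acts around that threshold, though these percentages are for 0.05.

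Point estimates, fully observed factors and clear-cut results are not in doubt. The size rests on the assumed FMI, on data missing at random, and on a logistic rather than a Cox model in the simulated cohort.

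**What to change.** In section 5.3 (4), replace m=5 with m=50, or with a number at least equal to the percentage of incomplete cases among the patients retained after the exclusions. Fix the random seed and report it, and use the same m and seed for the complete-case comparison in section 5.4.2 (6). At FMI 0.2 this brings the disagreement for a stable p of 0.03 from about 41% down to about 1%.

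The cost is computing time only. The mice package is already named in section 5.4.2, and no new data or patients are needed.
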